- Any other histological type of lymphoma, including primary mediastinal (thymic) large B-cell (PMBL) or Burkitt lymphoma
- A prior diagnosis of chronic lymphocytic leukemia (CLL) (Richter's Transformation)
- Primary central nervous system (CNS) lymphoma
- A history of secondary CNS involvement by DLBCL are ineligible, unless treated into remission

Exclusionary Previous and Current Treatment

- Subjects who have previously received treatment with an anti-CD20 × anti-CD3 bsAb
- Subjects who have been previously treated with tafasitamab
- Anti-CD20 therapy (eg, rituximab) within 21 days prior to Day –8, to minimize competition with plamotamab binding to CD20 on DLBCL target cells
- Subjects who have, within 14 days prior to Day –8:

- Chemotherapy, radiotherapy, or other lymphoma-specific therapy not including anti-CD20 therapy. Note: palliative local radiotherapy is permitted; however, these lesions may not serve as target lesions.
- Small molecule or investigational anticancer agents within 6 elimination half-lives prior to Day –8
- Undergone major surgery not related to lymphoma complications or suffered from significant traumatic injury
- Received live vaccines within 30 days of Day –8
- Required systemic anti-infective therapy for active, intercurrent infections
- Subjects who have had the following prior therapies or treatments:
 - Have, in the opinion of the Investigator, not recovered sufficiently from the adverse effects of prior therapy(ies)
 - Were previously treated with CD19-targeted therapy, including CAR-T, unless current biopsy (after last therapy) is CD19+
 - Have known intolerance to CD20 monoclonal antibody therapy
 - Have a history of hypersensitivity to compounds of similar biological or chemical composition to tafasitamab, immunomodulatory imide drugs (IMiDs), and/or the excipients contained in the study drug formulations
 - Have undergone autologous stem cell transplantation (ASCT) \leq 1 month prior to signing the informed consent form. Subjects who have a more distant history of ASCT must exhibit full hematologic recovery before enrollment into the study.
 - Have undergone previous allogenic stem cell transplantation
 - Have a history of deep venous thrombosis/embolism, threatening thromboembolism, or known thrombophilia, or are at high risk for a thromboembolic event in the opinion of the Investigator, and who are not willing/able to take venous thromboembolic event prophylaxis during the entire treatment period

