- ^q PET/CT and bone marrow biopsy/aspirate (for subjects with known bone marrow involvement). All studies for the baseline assessment should be performed within 21 days prior to Day -8. After Cycle 12, perform disease assessments every 3 cycles (or Q12 weeks) up to Cycle 36 and every 4 cycles (Q16 weeks) up to Cycle 60. Any unscheduled disease assessment performed in suspicion of progressive disease must be recorded in the eCRF.
- ^r PHI-redacted tumor assessments including, but not limited to assessment reports and/or digital imaging files (DICOM) for scans/imaging, blood, and bone marrow biopsy pathology reports are to be provided to support response assessments.
- ^s Archival tissue from excisional biopsies of lymph node to be sent to the designated central laboratory as an archival block (**preferred**) or up to 43, if possible, unstained slides. Archival tissue must predate study treatment. If archival tissue is not available or is insufficient, the screening fresh tumor biopsy becomes mandatory to satisfy the inclusion criterion.
- ^t Fresh tumor biopsy will be collected at screening up to 21 days prior to Day -8. The on treatment fresh tumor biopsy performed after the fourth dose between the C1D22 and C2D1 visit. Fresh tumor biopsy is strongly encouraged but is optional and requires separate consent. The baseline sample becomes mandatory for study participation if archival tissue is not available to satisfy the inclusion criterion.
- ^u The Screening (baseline) sample will come from the submitted archival or fresh tumor biopsy sample to identify malignant clones. Samples of whole blood and plasma will be collected through C2D1; only whole blood will be collected at C2D26, C6D1, C9D1, C12D1 and EOT for the detection and quantification of ID clonotype(s) that were identified from the baseline sample.

- ^v Male subjects will be followed for 6 months, and female subjects 8 months following the last dose of study drug to confirm contraceptive use.
- ^w Subjects who complete a tumor assessment within the prior 14 days do not have to repeat the EOT tumor assessment. If a subject was removed from study for disease progression and this response data for that applicable visit is adequately documented in EDC, the post-treatment (EOT and 90 days post EOT) tumor assessments do not need to be repeated.
- ^x Treatment-related SAEs should be followed up until resolution.

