- SARS-CoV-2 nucleic acid or antigen test (to be completed within 7 days prior to Day – 8)
- Urine or serum β -hCG pregnancy test for women of childbearing potential performed at screening (within 10 to 14 days of Day –8) and at Day –8 or an FSH test for postmenopausal women. An FSH test only needs to be performed once during screening to confirm that the subject is not capable of becoming pregnant.

- Lenalidomide Counseling is performed during screening prior to Day –8. Please see the supplemental Summary of Pregnancy Prevention Strategies, provided under separate cover, for details.
- The following are to be sent to the central laboratory per the laboratory manual:
 - Peripheral blood for T-, B-, and NK cells (TBNK); leukocyte flow cytometry to assess frequencies of circulating leukocytes; and for leukocyte phenotyping, function, and activation markers
 - Peripheral blood for ctDNA analysis to assess MRD (see [Section 8.2.1](#))
 - Archival blocks (preferred) or unstained slides for cell of origin determination by a central pathologist (see [Section 8.2.2.1](#))
 - Biopsy of disease site. Subjects will be consented and may undergo an optional (recommended) biopsy to obtain fresh tumor tissue (for those subjects with accessible superficial lymphadenopathy that can easily and safely be accessed) (see [Section 8.2.2.1](#) and [Section 8.2.2.2](#)).
- Tumor assessments will be performed by the Investigator using PET/CT or CT scans and bone marrow if bone marrow involvement is suspected or known. The same evaluations (ie, imaging, blood, bone marrow) performed at baseline will be performed at each subsequent disease assessment. All tumor assessments should be performed within 21 days prior to the first dose of Study Drug (Day –8). Tumor assessments must be read locally, and scans and other relevant information must be submitted to the central imaging designee for review by the BIRC. Redacted tumor assessments including, but not limited to, assessment reports and/or actual data (Digital Imaging and Communications in Medicine [DICOM] files) for scans, blood analysis, and bone marrow biopsy pathology reports may be requested by the Sponsor. If requested by the BIRC, additional information may be required, including the interpretation, differential, and addenda when available (flow cytometry, cytogenetics, FISH, and/or molecular testing.)
- Record AEs and concomitant medications

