9. ASSESSMENT OF EFFICACY

9.1. Efficacy Assessments

Table 16: Assessment of Response

Response	Site	PET-CT–Based Response	CT-Based Response
Complete	Lymph nodes and extralymphatic sites	Complete metabolic response Score 1, 2, or 3 ^a with or without a residual mass on 5PS ^b	Complete radiologic response (all of the following) Target nodes/nodal masses must regress to < 1.5 cm in LDi No extralymphatic sites of disease
	Nonmeasured lesion	Not applicable	Absent
	Organ enlargement	Not applicable	Regress to normal
	New lesions	None	None
	Bone marrow	No evidence of FDG-avid disease in marrow	Normal by morphology; if indeterminate, IHC negative
Partial	Lymph nodes and extralymphatic sites	Partial metabolic response Score 4 or 5 ^b with reduced uptake compared with baseline and residual mass(es) of any size	Partial remission (all of the following) > 50% decrease in SPD of up to 6 target measurable nodes and extranodal sites When a lesion is too small to measure on CT, assign 5 mm × 5 mm as the default value When no longer visible, 0 × 0 mm For a node > 5 mm × 5 mm, but smaller than normal, use actual measurement for calculation
	Non-measured lesion	Not applicable	Absent/normal, regressed, but no increase
	Organ enlargement	Not applicable	Spleen must have regressed by > 50% in length beyond normal
	New lesions	None	None
	Bone marrow	Residual uptake higher than uptake in normal marrow but reduced compared with baseline (diffuse uptake compatible with reactive changes from chemotherapy allowed). If there are persistent focal changes in the marrow in the context of a nodal response, consideration should be given to further evaluation with MRI or biopsy or an interval scan	Not applicable

Table 16: Assessment of Response (Continued)

Response	Site	PET-CT–Based Response	CT-Based Response
Stable or No response	Target nodes/nodal masses, extranodal lesions	No metabolic response Score 4 or 5 with no significant change in FDG uptake from baseline at interim or end of treatment	Stable disease < 50% decrease from baseline in SPD of up to 6 dominant, measurable nodes and extranodal sites; no criteria for progressive disease are met
	Non-measured lesion	Not applicable	No increase consistent with progression
	Organ enlargement	Not applicable	No increase consistent with progression
	New lesions	None	None
	Bone marrow	No change from baseline	Not applicable

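### The baseline PET/CT is not required to follow the last anti-lymphoma therapy, so ORR and CRR could include a small amount of response owed to pre-study treatment

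*Protocol*

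**What the plan says.** **Scan window.** Protocol Section 5, Table 9 footnote q: "All studies for the baseline assessment should be performed within 21 days prior to Day" -8. Section 7.5.1 repeats it: "All tumor assessments should be performed within 21 days prior to the first dose of Study Drug", which is Day -8.

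**Therapy window.** The exclusion criteria (synopsis and Section 6.2) open a list with "Subjects who have, within 14 days prior to Day" -8, and its first item is "Chemotherapy, radiotherapy, or other lymphoma-specific therapy not including anti-CD20 therapy". The same item then relaxes the rule for one modality: "Note: palliative local radiotherapy is permitted; however, these lesions may not serve as target lesions". Anti-CD20 therapy has its own 21-day bar, and small-molecule or investigational agents have a bar of 6 elimination half-lives.

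**Entry routes.** Section 6.1 requires at least one of two. The relapsed route needs progression documented after the most recent regimen. The primary-refractory route looks only at the outcome of first-line therapy. Primary-refractory subjects are capped at 36 of 200 in Part 2; no cap is stated for Part 1.

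**Response criteria.** In Section 9.1, Table 16, CT-based partial response is driven by target lesions. The PET-based complete response row ("Complete metabolic response Score 1, 2, or 3") and the PET-based partial response row (reduced uptake against baseline) apply to lymph nodes and extralymphatic sites, without limitation to targets.

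**The concern.** A baseline scan is the reference for response. If anti-lymphoma treatment can fall between that scan and the first study dose, a fall in uptake caused by the earlier treatment can be read as response to study drug. The protocol applies the right ordering elsewhere: after prior CD19-targeted therapy, CD19 status must come from a biopsy taken after the last therapy. The baseline scan has no equivalent rule.

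BIRC-assessed ORR is the first secondary test after PFS and stands ahead of OS and TTF (Section 11.3.4), with planned power of only 80%. CRR is also a secondary endpoint. Part 1 has no control arm, and the Part 2 sample size may be adjusted on Part 1 results. Spurious responses would raise observed rates in both arms, narrow the difference between them, and make Part 1 look somewhat better than it is.

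**Working it through.** **1. Dates.**
- Earliest valid baseline scan: Day -8 minus 21 days = Day -29.
- Therapy barred from: Day -8 minus 14 days = Day -22. Latest permitted non-anti-CD20 therapy: Day -23.
- Scan before systemic therapy: from Day -29 to Day -23 = up to 6 days.
- Scan before palliative radiotherapy: from Day -29 to Day -8 = up to 21 days.
- Anti-CD20 therapy: a 21-day bar against a 21-day scan window leaves no gap.

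**2. Who can be affected.** A relapsed subject treated after the scan would need a new documented progression after that treatment, which largely closes the systemic route. A primary-refractory subject with later therapy has no such requirement. Palliative radiotherapy is open to both groups.

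**3. What an irradiated site can do.** On CT it cannot be a target, so it cannot drive a partial response. On PET it could contribute to a reading of reduced uptake, or turn a partial into a complete metabolic response if every other site also clears. The second changes CRR but not ORR, because ORR = CR + PR.

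**4. The plan's own figure.** Section 11.3.3 gives 60% versus 78%, 100 per arm, one-sided 0.025 and 80% power. With a pooled null variance:
- mean rate = (0.60 + 0.78)/2 = 0.69
- SE under the null = √(2 × 0.69 × 0.31/100) = 0.0654
- SE under the alternative = √((0.60 × 0.40 + 0.78 × 0.22)/100) = 0.0642
- power = Φ((0.18 − 1.96 × 0.0654)/0.0642) = Φ(0.807) = 79.0%

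Unpooled variance gives 80.1%. The stated figure is reproduced.

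**5. Sensitivity.** The documents give no exposure rate, so both inputs here are assumptions. Let a share f of each arm be exposed, and let a share c of exposed non-responders be counted as responders. Then ORR in Arm B = 0.60 + 0.40fc and ORR in Arm A = 0.78 + 0.22fc.

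| f | c | Arm B | Arm A | Difference (points) | Power |
|---|---|---|---|---|---|
| 0 | – | 60.0% | 78.0% | 18.0 | 79.0% |
| 2% | 50% | 60.4% | 78.2% | 17.8 | 78.4% |
| 5% | 50% | 61.0% | 78.6% | 17.6 | 77.5% |
| 18% | 50% | 63.6% | 80.0% | 16.4 | 73.4% |
| 18% | 100% | 67.2% | 82.0% | 14.8 | 67.1% |

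At f = 5% and c = 50%, Arm B gains 100 × 0.40 × 0.05 × 0.50 = 1 responder and Arm A gains 100 × 0.22 × 0.05 × 0.50 = 0.55. The 18% rows are the full cap of 36/200 and bound the primary-refractory route only.

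**The case against.** The case against giving this much weight is strong, and most of it stands.

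- Response is scored per subject. Entry needs a measurable, PET-positive lesion, and irradiated lesions cannot be targets, which implies untreated measurable disease. One irradiated site turning negative cannot by itself give a complete metabolic response. A false partial response needs a reader to rely on that site while the others are unchanged.
- The systemic gap is about 6 days. Consent must precede screening tests (Section 7.5), concurrent anticancer treatment is excluded (Section 6.2), and the Medical Monitor or a designee reviews screening data before treatment or randomization (Section 7.4). Few subjects could receive chemotherapy between a study scan and Day -23.
- The BIRC includes a clinical reviewer (Section 4.9.2) and receives other relevant information with the scans (Section 7.5.1). An imaging charter is promised but is not among the documents, so its handling of irradiated sites is unknown, not shown to be missing.
- The windows are the same in both randomized arms.

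These points limit the size of the effect. They do not supply the missing ordering rule, and none says how an irradiated site counts on PET.

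A reader might infer three stronger things that the documents do not support:

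- **The target-lesion bar is irrelevant to PET.** Table 16 uses target in the shared site labels of the stable and progressive rows. Only the complete and partial response rows lack it.
- **ORR power drops to 67% to 76%.** Such figures count every affected subject as a responder. The 67% figure also needs every primary-refractory place to be filled and every such subject to be exposed.
- **Arm A is favoured.** With equal exposure, Arm B gains more, because it has more non-responders to convert.

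**Conclusion.** The gap is real and small. The plan as written lets the baseline scan precede the last anti-lymphoma treatment, and the existing safeguards narrow this without closing it. The remaining openings are primary-refractory subjects with later systemic therapy (up to about 6 days) and any subject given palliative radiotherapy (up to 21 days).

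Under moderate assumptions (2% to 5% exposed, half of exposed non-responders converted, equal exposure by arm), ORR rises by at most 1 point per arm and power falls from 79.0% to between 78.4% and 77.5%. CRR could be inflated separately where a partial response is read as complete; the documents give no basis for sizing that. The PFS sample size uses no response rate and is unaffected.

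SAP Sections 1, 4.1 and 7 record early termination with 3 subjects and listings only, so no ORR test will be run. The point matters for the design text and for reading any listed response.

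**What to change.** 1. In Section 7.5.1 and Table 9 footnote q, require the baseline tumor assessment to be done after the last anti-lymphoma therapy, including palliative radiotherapy, as well as within 21 days before Day -8. Reconcile this with the windows in Section 6.2 and the synopsis.
2. Record irradiated sites and dates and pass them to the BIRC. Section 7.2 captures medications and blood products from 21 days before Day -8 but does not name radiotherapy.
3. State in Section 9.1 that reduced uptake or shrinkage at an irradiated site alone does not count as response, while progression at that site still counts for PFS. Excluding irradiated sites from assessment altogether would be wrong, because it would also discard progression there and so alter the primary endpoint.

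Cost: a few screening scans booked later in the window or, rarely, repeated, and one added data field. The sample size does not change.

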1. LIST OF ABBREVIATIONS AND DEFINITIONS OF TERMS

The following abbreviations and specialist terms are used in this study protocol.

Table 1: Abbreviations and Specialist Terms

Abbreviations and Specialist Terms	Explanation
ABC	activated B cell
ADA	anti-drug antibodies
ADL	activities of daily living
ADR	adverse drug reaction
AE	adverse event
ALT	alanine aminotransferase
ANC	absolute neutrophil count
APTT	activated partial thromboplastin time
ASCT	autologous stem-cell transplantation
AST	aspartate aminotransferase
ASTCT	American Society for Transplantation and Cellular Therapy
β-hCG	beta human chorionic gonadotropin
BIRC	Blinded Independent Review Committee
bsAb	bispecific antibody
CAR-T	chimeric antigen receptor-modified T-cell therapy
CBC	complete blood count
CI	confidence interval
CLL	chronic lymphocytic leukemia
COO	cell of origin assay
CNS	central nervous system
CR	complete response
CRS	cytokine release syndrome
CT	computerized tomography
CTCAE	Common Terminology Criteria for Adverse Events
ctDNA	Circulating tumor DNA
C _{trough}	predose or trough concentration
DCF	Data Clarification Form
DICOM	Digital Imaging and Communications in Medicine
DLBCL	diffuse large cell B-cell lymphoma
DOR	duration of response
DP	drug product
ECG	electrocardiogram
ECOG	Eastern Cooperative Oncology Group
eCRF	electronic case report form

Abbreviations and Specialist Terms	Explanation
EDC	electronic data capture
EOI	end of infusion
EOS	end-of-study
EOT	end-of-treatment
FcγR	Fc gamma receptor
FDA	US Food and Drug Administration
FDG	fluorodeoxyglucose
FISH	fluorescence in situ hybridization
FSH	follicle-stimulating hormone
GCB	germinal center B-cell
GCP	good clinical practice
GGT	serum gamma-glutamyl transferase
HBcAb	hepatitis B core antibody
HBsAg	hepatitis B surface antigen
HBV	hepatitis B virus
HCV	hepatitis C virus
HEENT	head, eyes, ears, neck, and throat
HIV	human immunodeficiency virus
HR	hazard ratio
HSCT	hematopoietic stem cell transplantation
ICANS	immune effector cell-associated neurotoxicity syndrome
ICE	Immune effector cell-associated encephalopathy
ICF	informed consent form
ICH	International Council on Harmonisation of Technical Requirements for Pharmaceuticals for Human Use
IDMC	independent data monitoring committee
ICMJE	International Committee of Medical Journal Editors
IEC	Independent Ethics Committee
IgE	immunoglobulin E
IL-6	interleukin-6
IMiD	immunomodulatory agent
IMP	investigational medicinal product
IND	Investigational New Drug (Application)
INR	international normalized ratio
IPI	international prognostic index
IRB	Institutional Review Board
IRT	interactive response technology
IUD	intrauterine device
IUS	intrauterine hormone-releasing system

Abbreviations and Specialist Terms	Explanation
IV	intravenous(ly)
IVSS	Intravenous Solution Stabilizer
LEN	Lenalidomide
mAb	monoclonal antibody
MCV	mean corpuscular volume
MDRD	Modification of Diet in Renal Disease
MedDRA	Medical Dictionary for Regulatory Activities
MRD	minimal residual disease
NCI	National Cancer Institute
NHL	non-Hodgkin's lymphoma
NK	natural killer
NOS	not otherwise specified
OR	objective response
ORR	objective response rate
OS	overall survival
OUS	outside United States
PBML	primary mediastinal large B-cell
PD	progressive disease
PE	physical exam
PET/CT	combined positron emission tomography with computerized tomography
PFS	progression-free survival
PI	package insert
PK	pharmacokinetics
PO	by mouth
PR	partial response
PRR	partial response rate
PT	prothrombin time
Q2W	every 2 weeks
RBC	red blood cell
RDW	red blood cell distribution width
RP2D	recommended Phase 2 dose
R/R	relapsed or refractory
RTSM	randomization and trial supply management
SAE	serious adverse event
SAP	Statistical Analysis Plan
SARS-CoV-2	severe acute respiratory syndrome coronavirus 2 of the genus betacoronavirus
scFv	single-chain variable fragment (immunoglobulin fusion protein)

Abbreviations and Specialist Terms	Explanation
SD	stable disease
SmPC	Summary of Product Characteristics
SOC	System Organ Class
SUSAR	Suspected Unexpected Serious Adverse Reaction
TBNK	T-, B-, and NK cells
TEAE	treatment-emergent adverse event
TLS	tumor lysis syndrome
TTF	time to treatment failure
ULN	upper limit of normal
WBC	white blood cell
w/v	weight-to-volume

2. INTRODUCTION

2.1. Diffuse Large B-cell Lymphoma

Diffuse large B-cell lymphoma (DLBCL) is the most common subtype of non-Hodgkin's lymphoma (NHL). Since the introduction of the anti-CD20 antibody rituximab, approximately 50% to 70% of patients may achieve cure with initial standard-of-care immunochemotherapy. For patients who are refractory to or relapse after frontline therapy, prognosis is poor. Salvage chemotherapy followed by high-dose chemotherapy and autologous stem-cell transplantation (ASCT) has some benefit in this setting and is associated with significant toxicities. Moreover, most patients are ineligible for this approach and have fewer treatment options. Recent therapeutic advances, such as chimeric antigen receptor T-cell therapy (CAR-T) and tafasitamab (US: Monjuvi[®]; EU: Minjuvi[®]) plus lenalidomide (Revlimid[®]), have potential to improve patient outcomes. Despite these advances, a significant need remains to provide effective treatment options for patients with relapsed or refractory (R/R) DLBCL who are ineligible for ASCT (Coiffier, 2016).

2.2. CD20 as a Therapeutic Target

The introduction of the anti-CD20 monoclonal antibody (mAb) rituximab for B-cell lymphoma in the late 1990s inaugurated a new era of cancer therapy (Maloney, 1994). In principle, mAbs are an amalgamation of 2 desirable characteristics of an anticancer drug, and rituximab exemplifies these qualities. First, rituximab is a therapy targeted to the tumor cell and carries fewer side effects than chemotherapy. Second, with its ability to directly stimulate the host immune system, it can potentially induce stronger, more long-lasting anti-tumor effects that bypass immunosuppressive factors. CD20 is an ideal target for monoclonal antibody therapy, since most B-cell neoplasms consistently express it, but normal B lineage stem cells and plasma cells do not allow B-cell repopulation and immunoglobulin production to continue, at least over several years (Stashenko, 1980). Rituximab (Rituxan[®], Truxima[®], MabThera[®]) and other similar therapeutic anti-CD20 mAbs such as iodine-131 tositumomab (Bexxar[®]), ofatumumab (Arzerra[®] and Kesimpta[®]), and obinutuzumab (Gazyva[®]) have been largely effective in realizing these aims, with impressive efficacy coupled with modest toxicity (Illidge, 2015; Robak, 2016).

However, there are limitations to these gains. Approximately 30% of cases of B-cell NHL either do not respond to rituximab or relapse after initially responding, and eventually become refractory to rituximab (Stolz, 2009). Also, rituximab has good activity against tumor masses and circulating tumor cells but has significantly less ability to clear tumor from bone marrow and lymph nodes (Mraz, 2011). Clearly, the ability of rituximab to strongly activate immune killing of tumor cells needs to be improved, especially in certain compartments of the body, while maintaining its tolerable side-effect profile.

[figure not shown]
Resistance to anti-CD20 monoclonal antibody therapy also remains a problem, although the mechanism of this resistance is still somewhat unclear. Recently, new anti-CD20s have entered the clinic to address this issue. Ofatumumab (type I) and obinutuzumab (type II) were both approved by the United States Food and Drug Administration (FDA) in 2009 and 2013,

respectively, for the treatment of chronic lymphocytic leukemia (CLL; [Lee \[B\], 2014](#); [Lemery, 2010](#)). These antibodies have characteristics that theoretically should improve their efficacy over rituximab ([Alduaij, 2011](#); [Niederfellner, 2011](#); [Rafiq, 2013](#); and [Teeling, 2004](#)). The hope is that the new anti-CD20 mAbs will be more efficacious than rituximab, but the clinical data so far are mixed. One study of a head-to-head comparison between rituximab and obinutuzumab in relapsed indolent lymphoma showed no difference in progression-free survival (PFS; [Sehn, 2007](#)). In a head-to-head comparison in patients with CLL ([Goede, 2014](#)), obinutuzumab was superior to rituximab when combined with chlorambucil, but the doses and schedules of the 2 mAbs were not matched. In short, although in vitro and xenograft studies support the potential of the new anti-CD20 mAbs over rituximab, the available clinical data are unclear as to whether these new mAbs are indeed an advance.

